(3) Is the *improvised dressing* culturally acceptable to health care providers, patients, and families for managing SCLUs in Jamaica?

The expected study outcome is improvised dressing superior effectiveness and quality of life, when compared with usual practice, without increased safety and acceptability issues.^{13,59,60,62} The improvised dressing is likely to be the least expensive choice, with the added benefit of being available as first aid treatment throughout Jamaica. The advanced dressing is likely to be more expensive with respect to materials costs, although fewer dressing changes are anticipated and pain medication expenses are likely to be reduced. Based upon the review of the literature, no serious infections or other safety issues are anticipated for any group. However, to ensure that complications are not overlooked, in addition to the onsite researchers' vigilance, weekly wound photos will be assessed for complications (signs of infection, wound deterioration, or clinically relevant maceration) by two off-site blinded wound experts, Drs. [name] and [name].

Definitions:

Sickle cell leg ulcer – a wound in a HbSS or HbS β^0 positive patient, open greater than one month,⁷ below the level of the knee excluding the plantar surface of the foot.

Closed wound -100% epithelialized with no discernible scab or exudate production (paper napkin remains dry when lightly pressed against area, and no recurrence in the subsequent two weeks)

Safe – infection and other complications (healing-impairing maceration, keloid, and contracture rates) not statistically significantly higher than usual practice, with no major adverse events attributable to the method

Effective – ulcer closure rates or ulcer surface area reduction rates not statistically significantly lower than usual practice

Acceptable – average acceptability scores of 4 or higher on a 1-5 scale

3. Methods and Materials

a. Study design

This study will be a targeted-blinded (the off-site wound experts and the local physicians verifying wound closure and/or complications will be blinded to the randomization group), randomized controlled trial with three arms: (1) usual practice (negative control), (2) the improvised dressing, and (3) the advanced dressing (positive control). The expected outcome is improvised and advanced dressing superiority.

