Decrease in SCLU surface area will be used to answer research question 1. Conducting a power analysis for this study is challenging because only one study of SCLUs has demonstrated a statistically significant outcome, and the effect size was obscured by high standard deviations, which is a common problem in studies of wounds.⁸ Improvised plastic dressings similar to the study dressings were used in 49 chronic pressure ulcers in elderly patients, which are often slow to close, if they heal at all.⁶⁰ These two studies demonstrated a significant difference with confidence intervals of 99% with ~25 patients per group. Based upon these sample sizes and the Central Limit Theorem, it is reasonable to set the minimum sample size for this study at 30 patients per group,.^{88,89}

d. Variables

Dependent Variables (measured weekly - tools and permissions in appendices):

- 1. Persistent wound pain (using the Faces Pain Scale Revised (FPS-R))
- 2. Procedural (dressing change) wound pain
- 3. Amount of pain medication taken, including a total number of morphine equivalents plus non-opioid pain medications
- 4. Approximate time spent standing, or sitting with leg dependent without compression (estimated hours per week)
- 5. Patient overall quality of life (assessed with the ASCQ-Me Emotional, Pain, Social Functioning, Stiffness, and Sleep Impact Short Forms)
- 6. Patient wound-specific quality of life (assessed with the Wound QoL tool)
- 7. Materials costs (estimated, using lowest retail costs on Amazon.com for items not on the UWI price sheets)
- 8. Time spent performing dressing changes
- 9. Wound complication rates (e.g., wound infection, healing impairing maceration, wound deterioration)
- 10. Change in wound surface area (measured in cm² electronically using software that automatically corrects for skew, such as HealthEPix or WoundMatrix)⁹⁰

Dependent Variables (measured one time, at graduation from study)

- 11. Wound closure time, in weeks (see definitions; verified two weeks later. Omit patients whose wounds did not fully close they are included in 10., above.)
- 12. Acceptability of dressing choice patient (5 point Likert scale and qualitative free response)
- 13. Acceptability of dressing choice family member (5 point Likert scale and qualitative free response)
- 14. Acceptability of dressing choice UHWI staff (5 point Likert scale and qualitative free response)

Independent Variables (documented at initial study visit):

1. Patient gender

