- 2. Age of open wound prior to entrance into study (in weeks, patient/family report)
- 3. Previous ulcer treatments (if any)
- 4. Education level (in years)
- 5. Smoking or any use of nicotine (yes/no in past week)^{84,85}
- 6. Mid-arm circumference (a surrogate for nutritional status) 91,92
- 7. Initial area of SCLU in cm^2 (see methods for multiple adjacent SCLUs)
- 8. Initial depth of SCLU at deepest point, in cm
- 9. Anatomic location of SCLU
- 10. ASCQ-Me baseline scores (all measures see appendices)
- 11. Social isolation (lives alone, without nearby support)⁸⁶
- e. Inclusion and exclusion criteria

Inclusion Criteria:

- > Diagnosed with HbSS or HbS β^0 sickle cell disease
- > Ages 13 70 years at study initiation (able to comprehend and give consent)⁸²
- > Males and females, pregnancy is not an issue
- > Open wound below the knee, not including the plantar surface of the foot
- > Wound open for longer than one month (defined as a chronic SCLU)
- > Traumatic, spontaneous, or recurrent SCLU (all etiologies)

Exclusion Criteria:

- > Patient younger than 13 years of age at study initiation
- > Patient older than 70 years of age at study initiation
- Wound open for less than one month by conclusion of study enrollment period (acute wounds could be traumatic wounds unrelated to sickle cell diagnosis)
- ➤ Diagnosis of cancer, hypertension, or chronic renal failure⁸²
- ➤ Diabetes (will screen for undiagnosed diabetes)⁸²
- Active wound infection (evidenced by clinical signs of malodor, dark-colored or thick drainage, or significantly increased warmth at the periwound) which is not resolved by the conclusion of the study enrollment period
- Osteomyelitis (if osteomyelitis is suspected, an ESR will be drawn; > 70mm/h with high platelet levels and low serum albumin warrants a bone biopsy)^{93,94}

> Hydroxyurea use (may be a confound because it reduces inflammation and negates much of the pathology of SSD – may choose to abstain for the study)^{7,95}

f. Sampling

- i. All eligible participants who consent to the study will be included. Participants will be randomized into one of the three groups immediately after the initial cleansing/debridement of their SCLU by the nurse using an electronic random number generator (an app). Waiting until the study dressing is to be applied to generate the random number will provide allocation concealment.

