- Based upon previous studies and the Central Limit Theorem, an estimated 90 participants (~30 per group) may be required for the differences between groups to reach statistical significance.^{12,23,88,89,96} Up to 120 patients will be recruited to allow for a 25% dropout rate. Based upon the literature review, pain, costs, wound size, and quality of life are expected to be significantly improved using the improvised dressings. However, because SCLUs are, historically, very slow to heal and often enlarge, complete wound closure is not an expected outcome for all patients.

g. Procedures for recruitment and consent

The study will be advertised using free community information channels such as church bulletins and radio outlets. Social media sites such as the CAIHR Facebook page will also be employed. Qualifying patients in the SCU database from up to two years prior to the study initiation will be called by the UHWI surgical team, alerting them to the dates for registering to participate. Flyers will be posted at the SCU in advance. Consent will be obtained by a member of the research team while the potential participant is waiting to be seen for wound care.

h. Data collection

The site for this study is the surgical clinic dressing area at the University Hospital of the West Indies (UHWI), Mona, Jamaica. The adjacent Sickle Cell Unit (SCU) will refer any SCLU patients to UHWI during the study period. UHWI is consistently well staffed with competent Jamaican health professionals. The UHWI surgical team will lead the study. Relatively few Jamaicans live or work in air-conditioned environments, ^[data in appendices] allowing the results from this out-patient population to translate to less developed tropical countries.

To ensure consistency, members of the research team will practice until they can demonstrate competency with all three dressing change procedures and with explaining the study forms prior to study patient recruitment.

Enrollment in the study will begin within two weeks of the day the Principal Investigator arrives at the Mona campus and will close 60 days later, or when a maximum of 120 patients have enrolled. All sickle cell positive patients presenting to UHWI with lower leg ulcers during the enrollment period will be screened for eligibility to enter the study. Each patient's data will be recorded for a total of 12 weeks, or until their SCLU has been closed for 2 weeks, whichever comes first.

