Study patients will be randomized into groups 1, 2, or 3 immediately AFTER initial thorough wound cleansing/debriding by the nurse or physician. Randomization will be accomplished using an electronic random number generator (an app).

After a member of the UHWI surgical team performs the initial cleansing/debriding, the control group (1) will have their ulcer dressed as usually done at UHWI. Wounds are dressed with saline-soaked gauze, covered with dry gauze. One wrap of stretch gauze will hold the dressing in place. Patients will clean the wound by vigorously wiping with gauze soaked in homemade normal saline (1 tsp salt/500ml water bottle), center to edges, at each dressing change, unless already very clean. Clean wounds will simply be irrigated with normal saline at each dressing change. Patients experienced with using papaya for debridement of their ulcers may apply it only to the open wound, avoiding contact with the periwound, to remove slough or eschar. If patients observe green exudate, they are permitted to add one teaspoon of vinegar to their bottle of saline. Dressings in group (1) will be changed daily. The dressings will be soaked off if they become adherent.

After initial cleansing/debriding, patients in the improvised dressing group (2) will then have a thin layer zinc oxide paste applied to the dried periwound, carefully avoiding the open wound.⁹⁷ A piece of a clean new plastic bag (food-grade World Star 1 mil LD bags, or the equivalent, purchased from the Papine Market across John Golding Road from the University of the West Indies), cut slightly larger than the ulcer will be gently conformed to the moist wound contours and sealed onto the zinc oxide paste. The bag will be fenestrated with a small slit using a number 11 scalpel or clean scissors prior to placing it on the ulcer in order to allow excess fluid to escape. The edges of the slit will be approximated. Clean gauze will be placed lightly over the slit to capture escaping fluid. One wrap of stretch gauze will hold the dressing in place. Patients will be instructed to change the dressings daily, irrigating with normal saline at each dressing change.⁶

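### Drawing the random number late does not by itself secure the allocation concealment that section 3f claims, because nothing described makes the first draw binding or traceable

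*Combined protocol and SAP*

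**What the plan says.** All references are to the combined protocol and SAP.

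- **Method.** Section 3h: "Randomization will be accomplished using an electronic random number generator (an app". Section 3f gives the same tool and places the draw right after the first cleansing and debridement of the ulcer.
- **Claim.** Section 3f: "Waiting until the study dressing is to be applied to generate the random number will provide allocation concealment". Timing is the only reason offered.
- **Operator.** Section 3f reads "of their SCLU by the nurse using an electronic random number generator (an app". The nurse here may be the person who cleans the wound or the person who draws. Section 3h attaches the nurse or physician to the cleansing and names no operator.
- **Blinding.** Section 5 says that participants and research team cannot be blinded, because the team provides the wound care. The off-site experts and the verifying physicians are blinded (section 3a).
- **Size.** Section 3c: "it is reasonable to set the minimum sample size for this study at 30 patients per group". Section 3f is softer: "an estimated 90 participants (~30 per group) may be required", and "Up to 120 patients will be recruited to allow for a 25% dropout rate". Enrolment "will close 60 days later, or when a maximum of 120 patients have enrolled" (section 3h).
- **Arms.** Section 3a describes a "randomized controlled trial with three arms" and gives no ratio. Equal allocation is inferred from about 30 per group.

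**The concern.** Allocation concealment needs two things. Whoever enters the patient must not be able to foresee the assignment, and must not be able to change it once it is seen. Late drawing supplies the first. The sections describe nothing that supplies the second.

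The setting makes this matter. When the number is drawn, staff have already cleaned and seen the ulcer. They will know the assignment and deliver the treatment. Section 3a states an expected direction of result, and section 4 discloses that a member of the research team is employed by the maker of one study dressing and relies on rigorous design as the safeguard. If draws could be altered, selection could enter at baseline. Blinded outcome assessment cannot remove that, and the ANCOVA of section 3i adjusts only for the characteristics that were recorded.

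A secondary question is whether the described method can be relied on to deliver the minimum of 30 per group.

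**Working it through.** **Step 1. Set the claim beside the method.**

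| Needed for concealment | Described in 3f or 3h? |
|---|---|
| Next assignment not foreseeable at consent | Yes: drawn after consent and debridement |
| Sequence fixed in advance | Not described |
| Rule linking number to arm | Not described |
| Person independent of the care who holds or releases assignments | Not described |
| Record of every draw | Not described |
| First draw binding | Not described |

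The first row is met. The others are what would show that the recorded assignment is the one first drawn.

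**Step 2. Reproduce the plan's own figure.** Inputs: 90 needed and 25% dropout (section 3f). 90 / (1 − 0.25) = 120, as stated. The 30 per group cannot be reproduced, because no effect size, standard deviation or power is given.

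**Step 3. Arm sizes under simple draws.** Assumption: each patient has probability 1/3 per arm. The probability of arm sizes a, b, c with a + b + c = n is n! / (a! b! c!) × (1/3)^n, summed over all cases with a, b and c at least 30.

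| Randomized, before dropout | P(all arms at least 30) |
|---|---|
| 90 | 0.9% (only 30/30/30 qualifies) |
| 100 | 40.6% |
| 110 | 78.6% |
| 120 | 94.3% |

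The standard deviation of one arm's size is √(n × 1/3 × 2/3), which is 4.5 at n = 90 and 5.2 at n = 120.

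**Step 4. Completers.** These matter because section 3a limits the non-inferiority analysis to patients who complete their assigned treatment. Assumption: 120 randomized, with dropout independent of arm and of other patients. For simple draws, the step 3 probability is averaged over a binomial number of completers. For exact 40/40/40 allocation, it is P(Binomial(40, 1 − dropout) ≥ 30) cubed. At 25% dropout the latter is 0.584³ = 0.199.

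| Dropout | Simple draws | Blocked 40/40/40 |
|---|---|---|
| 10% | 71.7% | 99.6% |
| 15% | 48.9% | 91.3% |
| 20% | 23.4% | 59.1% |
| 25% | 6.4% | 19.9% |

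**Step 5. Power cost of imbalance.** Power = Φ(d / √(1/n₁ + 1/n₂) − 1.96), two-sided 5%, with an illustrative effect of d = 0.65 standard deviations.

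- 30 against 30: 0.65 / 0.2582 − 1.96 = 0.557, power 71.1%.
- 24 against 36: 0.65 / 0.2635 − 1.96 = 0.507, power 69.4%.

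For d from 0.5 to 0.74 the loss is 1.6 to 1.8 percentage points.

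**Step 6. Predictability of blocks.** In a simulated 120-patient trial with blocks of 3, 6 and 9 in two strata, guessing the least-used arm in the stratum is right about 55% of the time, against 33% for simple draws. The unblinded team at this single site sees every past assignment, so it could make such guesses.

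**The case against.** The strongest defence is that unpredictability is the core of concealment and that the plan has it. Consent comes first, the draw comes last, and section 3f includes every eligible patient who consents. This stands as far as it goes. What remains is whether the draw is tamper-resistant and can be audited, which is narrower than having no concealment at all. It is still part of what section 3f asserts.

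Several stronger readings are tempting, and the documents do not support them:

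- *The treating nurse makes the draw.* Section 3f is ambiguous on this and section 3h names no operator. The gap is that no independent operator is specified.
- *Randomization is unrestricted and there is no list or log.* The sections are silent, an app could apply blocks, and the appendices were not available for this review. One can say only that such features are not described.
- *Draws will be manipulated.* Nothing suggests this. The point is that it could not be ruled out afterwards.
- *The plan promises 30 per group from the app and will miss it.* No section says that the app yields 30, and section 3f says about 30. The 0.9% at 90 patients reflects a condition that only one exact split can meet.
- *Blocking would cure the shortfall.* At 25% dropout, equal arms still miss 30 completers somewhere about 80% of the time. The main cause is a dropout allowance with no slack.
- *Ulcer size is left to chance, so stratification is needed.* Initial area is already a listed independent variable (section 3d), and the ANCOVA in section 3i controls for relevant ones.

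**Conclusion.** The point holds for concealment. Section 3f credits timing with more than timing can deliver, and the method as described leaves an assignment open to untraceable change by an unblinded team. How much bias could follow cannot be computed from the documents. The remedy is cheap, and allocation cannot be repaired once patients are enrolled.

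The arm-size part is minor. If 120 enrol, at least 30 are randomized to each arm about 94% of the time, so the intention-to-treat set would usually meet the figure. However, 120 is a ceiling, and enrolment may close at 60 days with fewer. With 25% dropout, all three arms keep 30 completers about 6% of the time. The power lost through imbalance of the kind shown is under 2 points. These figures assume simple 1:1:1 draws, dropout independent of arm, and illustrative effect sizes. The concealment conclusion depends on none of them. It would change only if an appendix describes a fixed, logged and independently held allocation.

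**What to change.** 1. Replace the app draw with a 1:1:1 list generated before enrolment by the off-site biostatistician already engaged (section 3i) and not shown to the clinic team.
2. Release assignments one at a time, either in sequentially numbered opaque sealed envelopes or through a date-stamped log. Do this only after consent, eligibility and baseline data are recorded. The planned timing, just before dressing, can stay.
3. State that the first assignment released is binding, and say who releases it.
4. Withdraw the statement in section 3f that timing alone provides concealment.
5. In section 3c, describe 30 per group as an approximate target, in line with section 3f.

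Blocking is optional: it evens out the arms but raises predictability in an open single-site trial. Stratification by ulcer area is not needed.

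The cost is a small amount of preparation: one list and, if envelopes are used, 120 of them. Without strata, a single sequence is enough.

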A Test of the Safety, Effectiveness, and Acceptability of an Improvised Dressing for Sickle Cell Leg Ulcers in a Tropical Climate

NCT04479618

As of June 3, 2021

IV. Project Proposal

1. Introduction:

a. Review of Literature

Sickle Cell Leg Ulcers:

One in 300 Jamaicans have the most serious form of sickle cell disease (HgbSS), and of these, between 30% and 70% will suffer from sickle cell leg ulcers (SCLUs).^{1-4,10} Although leg ulcers can affect any age group, by far the majority of sufferers develop their first SCLUs when they are between the ages of 10 and 19.^{2,18}

The SCLUs occur in a younger population, so comorbid conditions such as hypertension, diabetes, peripheral arterial or venous disease, and congestive heart failure are uncommon.¹⁶

SCLUs are found most often along the malleoli, followed by the shins.^{8,10} SCLUs heal 16 times slower than notoriously difficult to heal venous leg ulcers, and in some patients, they never heal, even with decades of expert wound management.^{3,5–7,16} SCLUs often enlarge during the first four weeks of management, and when they do close, they have a higher incidence of recurrence.^{8,16}

SCLUs have an even more negative impact on patient physical quality of life when compared to a myocardial infarction, kidney dialysis, or diabetic foot ulcer.¹⁷ Pain is unrelated to SCLU size and required high doses of opioid, which does not always provide adequate control.^{3,9,11,15,18,19} Because SCLUs often compromise education and employment opportunities, improving wound care for this population benefits the entire community in which they live.^{9–11}

Singh and Minniti, and Clare, Serjeant, et al., defined chronic SCLUs as those with greater than one month duration.^{3,20} Factors affecting the formation and healing of SCLUs or progression to a chronic condition remains elusive.²¹ The correlation with poverty, high serum lactate dehydrogenase, and lower leg venous system damage with SCLUs has been reported.^{3,7,10,18,20} Higher base line hemoglobin levels offer a protection against SCLUs.³ Slough, which is a byproduct of inflammation, is a hallmark of these chronic wounds.^{4,22} Compression therapy and bedrest improve healing of SCLUs, just as they improve the healing of venous ulcers not associated with sickle cell disease.^{3,15,18}

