Weekly, de-identified photographs will be sent by the Principal Investigator to be viewed by two blinded wound experts ([name] and [name]) off site. If the blinded experts, or anyone else involved in the study, expresses concern that a patient is exhibiting signs of possible infection, maceration that is delaying healing, or wound deterioration, a physician at UHWI or the SCU who is not otherwise involved in the study will be asked to evaluate that patient. The patient's dressings will be removed prior to this evaluation so that their treatment group will not be revealed to the physician (the evaluation by the physician is thus blinded to treatment group). If the physician determines that the patient's condition has not improved with the prescribed treatments (e.g., antibiotics), the patient will be withdrawn from the study. Any

patient who transitions out of the group to which they were randomized for any reason will receive usual treatment for their ulcer for the remainder of their 12 week study period.

When the treatment personnel at UHWI or the blinded remote observers state that the patient's wound appears to be closed, a physician at UHWI or the SCU who is not otherwise involved in the study will be asked to evaluate that patient. The patient's dressings will be removed prior to this evaluation so that their treatment group will not be revealed to the physician. Wound closure is defined as 100% epithelialized with no discernible scab or exudate production (a paper napkin blotting the area remains dry). Patients will be reassessed two weeks later to verify that the wound was truly closed and did not immediately recur.

Patients who are diagnosed with wound closure or have completed the 12 week study period will be taken aside privately and asked to rate the acceptability of their treatment using a 5 point Likert Scale. A family decision-maker will also be privately asked to rate the acceptability of the treatment. One of the research team members will enter this basic acceptability data for the patient and the family on the patient's Data Collection Tool. At that point, the patient will graduate from the study. However, patients and families will be instructed to return to UHWI for follow-up if a complication or recurrence develops. Any delayed complications (e.g., recurrence within 3 months) will be recorded on the patient's Data Collection Tool by the nurse or physician to whom the patient reports it.

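### Weekly recording stops two weeks after closure, so late pain, medication and quality-of-life values go missing according to response and question 2 can be misjudged

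*Combined protocol and SAP*

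**What the plan says.** Section 3h (Data collection) sets the recording period: each patient's "data will be recorded for a total of 12 weeks, or until their SCLU has been closed for 2 weeks, whichever comes first". Later in the same section, patients diagnosed with closure, or who have reached 12 weeks, rate the acceptability of their treatment, and then "At that point, the patient will graduate from the study". The paragraph before that says: "Patients will be reassessed two weeks later to verify that the wound was truly closed and did not immediately recur". After graduation one kind of information is still collected: "Any delayed complications (e.g., recurrence within 3 months) will be recorded on the patient's Data Collection Tool". This relies on the patient coming back, as patients and families are told to do.

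Section 3d (Variables) lists ten outcomes measured weekly. They include persistent and procedural wound pain, pain medication, time with the leg dependent, the ASCQ-Me forms and the Wound QoL. Section 2 uses several of these for question 2. For the area outcome, section 3c says: "Decrease in SCLU surface area will be used to answer research question 1".

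Section 3i (Statistical analysis) plans t tests, ANOVA and ANCOVA on each dependent variable, by intent-to-treat for superiority. It names no analysis week, no per-patient summary of the weekly values and no scoring of weeks after closure.

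**The concern.** Closure is an outcome that the dressing is meant to affect, and the plan expects the improvised dressing to outperform usual practice. A rule that ends recording after closure makes the late-week data missing because of treatment response. Intent-to-treat analysis cannot be carried out at those weeks, because the values of the early closers were never collected.

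Some outcomes can reasonably be filled in. Area is 0 while the ulcer stays closed. Pain medication, the ASCQ-Me forms and activity cannot be assumed to be zero or normal in a sickle cell patient with a closed ulcer. The study ulcer is also only the largest one (section 3c). If the stop rule refers to the study ulcer, a graduate may still have other open ulcers and still be dressing them.

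At stake is question 2. Depending on which summary is chosen, the same data could understate or overstate the benefit, and the plan leaves that choice open.

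**Working it through.** **The plan's own figures.** There is no stated closure rate, pain level or proportion expected to lack week-12 data. The nearest figure is the dropout allowance in section 3f: 90/(1 − 0.25) = 120, which reproduces. The plan does not say that this covers patients who leave because they healed.

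**Weeks lost.** Recording runs to week c + 2, so 12 − (c + 2) = 10 − c weeks are lost. Closure in week 4 loses 6 of the 12 weeks. Closure in week 10 or later loses none.

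**Assumed inputs (none from the documents).** Pain is on a 0–10 scale, 5 while open and 1 once closed. The dressing acts only through closure. Closure by week 12 is 20% in usual practice and 40% in the improvised group, with closure weeks spread evenly over weeks 3 to 12. Differences are improvised minus usual practice.

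**Week 12, everyone followed.**
- Improvised: 0.40×1 + 0.60×5 = 3.4
- Usual practice: 0.20×1 + 0.80×5 = 4.2
- Difference: −0.80

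**Week 12, recorded values only.** Of the ten closure weeks, only 10, 11 and 12 leave a week-12 record, so 3/10 of closers remain. Those without a record are 0.7×40% = 28% against 0.7×20% = 14%.
- Improvised: (0.12×1 + 0.60×5)/0.72 = 4.33
- Usual practice: (0.06×1 + 0.80×5)/0.86 = 4.72
- Difference: −0.39

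**Other closure rates, same method.**

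| Closure, usual vs improvised | True week 12 | Recorded week 12 |
|---|---|---|
| 5% vs 15% | −0.40 | 4.295/0.895 − 4.765/0.965 = −0.14 |
| 10% vs 30% | −0.80 | 3.59/0.79 − 4.53/0.93 = −0.33 |
| 20% vs 40% | −0.80 | −0.39 |
| 20% vs 50% | −1.20 | 2.65/0.65 − 4.06/0.86 = −0.64 |

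If less painful ulcers tend to close first, less survives. In a simulation with an assumed correlation of 0.5 between pain level and tendency to close, the recorded benefit was 0.02 of 0.30 at 5% vs 15%, and 0.13 of 0.66 at 10% vs 30%.

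**Other summaries, 20% vs 40%.** The groups differ by 0.20 in the proportion closing. An unhealed patient totals 12×5 = 60.
- *All 12 weeks:* a closer totals 5(c − 1) + (13 − c), on average 38. The saving is 22 per closer, so the group difference is 0.20×22 = 4.40 in the total and 4.40/12 = 0.37 in the mean.
- *Total over recorded weeks:* 5(c − 1) + 3 up to c = 10, then 52 and 56. The average is (244 + 52 + 56)/10 = 35.2. The difference is 0.20×24.8 = 4.96, which overstates 4.40.
- *Mean over recorded weeks:* [5(c − 1) + 3]/(c + 2) up to c = 10, then 52/12 and 56/12. The average is 3.676. The difference is 0.20×(5 − 3.676) = 0.26, which understates 0.37.
- *Last recorded value:* 1 for every closer. The difference is 0.20×4 = 0.80, with no loss, provided that the healed state lasts to week 12.

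**If graduation is at the diagnosis of closure.** Only closures in week 12 itself would then leave a week-12 record: (0.04×1 + 0.60×5)/0.64 − (0.02×1 + 0.80×5)/0.82 = 4.75 − 4.90 = −0.15 of −0.80.

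**The case against.** A reader might infer that late-week comparisons are made only among unhealed patients, so that the whole effect vanishes. The documents do not support that. Section 3h records two weeks after closure, so recent closers are still present at every week. Under the assumptions above, the week-12 difference would be 0 only if every closure came by week 9.

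A reader might also infer that the bias always runs towards no difference. It does not: a last recorded value can keep the full credit, and totals can overstate it. Because section 3i names no summary, the direction is not fixed.

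The illustration is also selective, since the plan expects less painful dressing changes while the ulcer is still open. If the improvised dressing also lowered open-ulcer pain by an assumed 0.5, the recorded difference would be (0.12×1 + 0.60×4.5)/0.72 − 4.72 = −0.80 of a true 3.1 − 4.2 = −1.10. The proportionate loss is smaller. The plan also says that closure is not expected for all patients, so few may graduate early.

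Persistent pain is defined as wound pain, and scoring it as zero after closure is arguable. The point is stronger for medication and ASCQ-Me.

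Recurrence is not ignored. Closure requires two weeks without it, and patients are told to return. But later capture is passive, and section 1a says of these ulcers that "when they do close, they have a higher incidence of recurrence". That comparative statement is enough to make a carried-forward healed value doubtful.

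These points limit the size and certainty of the effect. They do not supply the missing values or choose the analysis.

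**Conclusion.** The concern holds in a conditional form. The stop rule makes late weekly values missing according to response to the assigned dressing, and nothing in sections 3d, 3h or 3i fills them or says how to score them. For question 2, a late-week comparison or a mean over recorded weeks would understate the benefit of a dressing that closes more ulcers.

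Under the stated assumptions, with closure unrelated to pain level, roughly a third to a half of the week-12 difference survives. At 20% vs 40% closure, a mean over recorded weeks keeps 0.26 of 0.37. All these sizes rest on assumed closure rates, timing and pain levels.

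It would go too far to say that the randomised comparison is lost altogether. Early weeks are largely intact, and area for question 1 is known to be 0 while the ulcer stays closed. The change should be made before the data are collected, because uncollected values cannot be recovered.

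**What to change.** 1. Change the recording rule in section 3h so that every randomised patient provides the weekly sheet (pain, medication, activity, ASCQ-Me, Wound QoL) through week 12, by WhatsApp or in clinic, including after closure. Record area as 0 while closed and re-measure it if the ulcer reopens.
2. In section 3i, analyse the weekly outcomes in all randomised patients through week 12, with one prespecified time point or summary for each.
3. Reconcile the statements in section 3h on whether graduation comes at the diagnosis of closure or after the two-week check.

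If follow-up after closure proves impossible, prespecifying the estimand and the scoring of post-closure weeks is a weaker substitute. It makes the assumption visible but does not test it.

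The cost is small. Under the assumed closure weeks, a closer misses on average (7+6+5+4+3+2+1)/10 = 2.8 sheets. With 30 patients per group that is 0.40×30×2.8 ≈ 34 extra sheets at 40% closure and 0.20×30×2.8 ≈ 17 at 20%. Each takes at most the 30 minutes a week given in section 4. Early closers may also need a monthly visit, which section 4 puts at half a day. The WhatsApp route exists, and phone cards are already planned for all three 4-week periods.
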